5.1. Randomized Treatment Assignment

Randomization will occur using an automated online system that will reveal assignment group only after investigator/study staff have confirmed eligibility. The system will automatically send the participant study ID number and randomized treatment group assignment to the study pharmacist.

5.2. Active or Placebo Study Drug Doses and Schedule

The study protocol plans for randomized participants to receive 6 months of active drug OR 6 months of placebo.

5.2.1. Active Study Drug

Inhaled beclomethasone (QVAR®, Teva Pharmaceuticals) 320mcg twice daily for 180 days. The first dose will be administered 7 ± 3 days after CARV infection.

5.2.2. Placebo Study Drug

The first dose of placebo for inhaled beclomethasone (provided by Teva Pharmaceuticals) will be administered 7 ± 3 days after CARV infection.

5.2.3. Packaging and Labeling of Study Drug

All packaging and labeling will be completed by the investigational drugs pharmacy. The pharmacist(s) will prepare the study drug (active therapy or placebo) for administration to randomized participants based on treatment assignment. The study pharmacist(s) will label each drug kit with the participant's study identifier information, study information, appropriate drug/placebo information, and administration instructions.

5.2.4. Handling and Dispensing

Handling and dispensing of drug will occur by the study pharmacist(s) in the investigational drugs pharmacy. The study pharmacist(s) will store the study drugs in a secure area, and they will follow local and FDA regulations. The study pharmacist(s) will ensure that the study drugs are stored in the appropriate environmental conditions. Only authorized personnel will dispense study drug, and they will follow local and FDA regulations.

5.2.5. Blinding

The study pharmacist(s) practicing in the Investigation Drugs Service will remain aware of treatment allocation/assignment. Lung transplant clinical pharmacists, non-pharmacist study staff, the participants, and those involved in clinical care or study testing will remain blinded to treatment assignment (double-dummy design).

5.3. Immunosuppression

Patients' induction and maintenance immunosuppression will be prescribed and managed according to our transplant program's standard clinical practice. Likewise, we will treat and manage acute rejection, lymphocytic bronchiolitis, and BOS according to our standard clinical practice.

5.4. Treatment of CARV Infection

The decision to institute antiviral therapy specific for CARV infection and the choice of agent will be based on our program's standard clinical practice. Influenza is generally treated with oseltamivir. Respiratory syncytial virus (RSV) and parainfluenza virus (PIV) are generally treated with aerosolized ribavirin according to our standard clinical practice. Human metapneumovirus (hMPV) is sometimes treated with aerosolized ribavirin and intravenous immunoglobulin depending on the severity of the associated illness. The study will not influence the decision to treat with specific antiviral therapy nor the choice of agents.

In addition, all patients with a decline in pre-CARV baseline FEV₁ of $\geq 10\%$ will receive oral prednisone (1 mg/kg) orally daily (maximum of 60mg), initiated per standard protocol at the time of CARV infection. This dose will be rapidly tapered over two weeks back to the patient's pre-CARV maintenance prednisone dose.

At study entry, for the purposes of baseline CARV infection characterization, patients will receive a diagnosis of either upper or lower respiratory tract infection. Lower respiratory tract infection will be defined according to the ISHLT criteria as follows:

- ≥ 2 clinical symptoms (fever $> 38^{\circ}\text{C}$, rhinorrhea, nasal congestion, sore throat, sneezing, chills/rigors, myalgia, headache) PLUS one or more of the following symptoms of lower respiratory tract involvement:
 - Cough
 - Dyspnea
 - Physical findings (one or more of the following):
 - Hypoxia (new onset or increasing)
 - New or increased O₂ requirement
 - New crackles, rales, wheezing
 - Acute respiratory distress syndrome
 - Decline in pre-CARV baseline FEV₁ by $\geq 10\%$
 - Viral pathogen detected from bronchoalveolar lavage specimen

6. Testing

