Protocol:

A randomized placebo controlled trial of inhaled beclomethasone after community-acquired respiratory viral infection in lung transplant recipients

Version: 5

Date: 5.28.15

1. Abstract

The randomized placebo controlled trial of inhaled beclomethasone after community-acquired respiratory viral (CARV) infection in lung transplant recipients is a single center pilot study evaluating the impact of inhaled beclomethasone on the development and progression of chronic lung allograft dysfunction (CLAD) or death after CARV infection. The study will randomize 40 subjects to inhaled beclomethasone or placebo in a 1:1 ratio, and follow-up will be complete 12 months after randomization. The primary objective of the study is to determine if inhaled beclomethasone has greater efficacy than placebo for the endpoint of CLAD development or progression or death after randomization. The study will also assess multiple secondary endpoints including the safety and tolerability of inhaled beclomethasone in lung transplant recipients, respiratory viral symptom scores, the development of donor-specific human leukocyte antigen antibodies and antibodies to lung-specific self-antigens, and survival.

2. Background

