6.2. Spirometry

Subjects will have spirometry testing at the time of CARV infection and on months 1, 3, 6 and 12 (all $+/- 10$ days) following CARV infection. In addition, spirometry will be performed every 1-2 months ($+/- 10$ days) until month 12. Participants will also undergo spirometry testing when clinically indicated (new respiratory symptoms, pulmonary infiltrates, etc). Certified and trained technicians will conduct spirometry measurements according to American Thoracic Society (ATS) guidelines.

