6.5. Testing for Antibodies to Self-antigens and Inflammatory Cytokines

At the same time points that testing is conducted for DSA (enrollment and months 1, 3 and 6 [\pm 10 days for each time point]), participants will be tested for the development of antibodies to collagen V and K- α 1 tubulin. In addition, participants' serum will be tested for a battery of pro-inflammatory and anti-inflammatory cytokines. This will be conducted in [name] research laboratory.

7. Statistical Considerations

We estimate an incidence of new or progressive CLAD of 50% at 6 months after CARV infection in the placebo group and an absolute risk reduction of 25% in the inhaled beclomethasone group. Therefore, a sample size of 40 subjects would provide 80% power. The primary endpoint of the development or progression of CLAD or death at 6 months will be evaluated as a binary endpoint and will be analyzed using the chi-squared method. In addition, the primary endpoint will be evaluated as a time to event analysis using the Kaplan-Meier method and the two groups will be compared using the log rank test. Secondary endpoints consisting of continuous data will be analyzed using either the Student's t-test or Mann-Whitney U Test and those consisting of categorical data will be analyzed using the chi-squared method.

8. Ethical Considerations and Safety

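### The primary tests ignore both the BOS randomization stratum and the pre-treatment FEV1 fall; pre-specified stratification would guard against chance imbalance at little cost

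*Combined protocol and SAP*

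**What the plan says.** - **Entry spirometry (section 6.2).** "Subjects will have spirometry testing at the time of CARV infection", and then at follow-up visits.
- **Use of the fall at entry (section 5.4).** The section sets a rule for "all patients with a decline in pre-CARV baseline" FEV1: a fall of 10% or more determines an additional treatment at the time of infection. It is also one of the criteria for lower tract disease: at study entry "patients will receive a diagnosis of either upper or lower respiratory tract infection".
- **Timing (sections 5.2.1 and 5.2.2).** The first dose in either arm is planned 7 ± 3 days after CARV infection, so the entry FEV1 should precede treatment.
- **Endpoint (section 4.10).** Progressive CLAD is a decrement of at least 15% from the pre-CARV baseline FEV1 or FVC. New CLAD is FEV1 and/or FVC at or below 80% of a baseline that the section does not define, on two measurements 3 weeks apart.
- **Randomization (section 4.8).** 1:1, stratified by BOS group only (0 and 0p against 1 and 2).
- **Analysis (section 7).** The primary endpoint "will be evaluated as a binary endpoint and will be analyzed using the chi-squared method", with a second analysis by Kaplan-Meier and log-rank. Neither is described as stratified or adjusted, for the fall or for BOS group.

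**The concern.** A patient who enters 10% below the pre-CARV baseline is already 10/15, or two thirds, of the way to the progression threshold. Section 4.10 states no confirmatory measurement or minimum interval for progression. The fall is therefore a plausible strong predictor of the endpoint by construction, at least for progressive CLAD.

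Randomization does not balance it, and with about 20 patients per arm a visible imbalance will be common. If one appears, the unadjusted result will be hard to interpret, and an adjustment chosen after seeing the data will not be credible. BOS group is balanced by design, but the analysis does not use it either. What is at stake is some precision, and the credibility of the result in the one trial that is actually run.

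**Working it through.** **Inputs from the documents.** Section 1: "The study will randomize 40 subjects to inhaled beclomethasone or placebo in a 1:1 ratio", so 20 per arm. Section 7: "We estimate an incidence of new or progressive CLAD of 50% at 6 months after CARV infection in the placebo group". The same sentence assumes a reduction of 25 percentage points on active treatment, so 50% against 25%, taken here as the risks of the composite endpoint. The alternative in section 4.2 is two-sided. Alpha is not stated; 0.05 is assumed.

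**Inputs assumed, because the documents give none.** Prevalence of the fall 50%; 30% of patients in BOS 1-2, balanced by arm and not prognostic; a constant treatment odds ratio across levels of the fall, set so that overall active risk is 25%. Placebo risk with and without the fall: 75% and 25% (odds ratio (0.75/0.25)/(0.25/0.75) = 9), 65% and 35% (about 3.4), or 50% in both (no prognostic value).

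**Step 1: the plan's own figure.** Section 7 states: "Therefore, a sample size of 40 subjects would provide 80% power". The normal-approximation power for two proportions is

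Φ{[|p1 − p2|√n − 1.96√(2p̄(1 − p̄))] / √(p1(1 − p1) + p2(1 − p2))}.

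With p1 = 0.50, p2 = 0.25, p̄ = 0.375 and n = 20, this is Φ{(1.118 − 1.342)/0.661} = Φ(−0.34), or about 36.8%. Exact enumeration of the chi-squared test gives 37.5%. The stated 80% is not reproduced; it would need 58 per arm (116 in total). The starting point for any gain is therefore about 37%.

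**Step 2: how often the arms differ.** If each patient has the fall with probability 0.5, the arms differ by 4 or more patients (20 percentage points) in about 27% of trials. If exactly 20 of the 40 have the fall, the figure is 34%; at 30% prevalence (12 of 40) it is 30%.

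**Step 3: null error.** Simulated at 20 per arm with no treatment effect and the 75%/25% factor:

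| Trials | Unadjusted chi-squared | Four-stratum Mantel-Haenszel |
|---|---|---|
| All | about 4.3% | about 5% |
| Imbalance of 4 or more (27%) | about 8.6-8.9% | 4.9% |
| Remaining (73%) | about 2.8% | – |

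The unadjusted rows agree with each other: 0.27 × 8.6% + 0.73 × 2.8% = 2.3% + 2.0%, or about 4.4%, which matches 4.3% within rounding and simulation error. With the 65%/35% factor, the unadjusted error in imbalanced trials is only about 5.7-5.9%.

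**Step 4: power at 50% against 25%.**

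| Placebo risk with / without the fall | Unadjusted | Four strata (fall × BOS) |
|---|---|---|
| 75% / 25% | about 37% | about 42% |
| 65% / 35% | about 37% | about 38% |
| 50% / 50% | about 37% | about 35% |

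Stratifying by the fall alone gives about 44% and 39% in the first two rows, so adding BOS costs a point or two when BOS is not prognostic.

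**Step 5: cross-check with another method.** Linear-model adjustment for the continuous FEV1 fall gives power of about 36% with no prognostic value, 39% at an odds ratio of 2 per SD, 43% at 3 and 48% at 5. The pattern is the same. A logistic likelihood-ratio test gives more power, but its null error is about 6%. The Mantel-Haenszel test holds its size.

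**The case against.** The strongest case against is that nothing here is an error. An unadjusted chi-squared test is valid in a randomized trial, and a pilot may choose the simplest test. That stands. Three stronger readings are tempting, and the documents do not support them.

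- **That the planned test inflates false positives.** The 8.6-8.9% applies only to the 27% of trials with a marked imbalance. The other 73% offset it at about 2.8%, and the overall rate of about 4.3% is below nominal. Stratification in fact raises the overall rate slightly, to about 5%.
- **That a useful power gain is assured.** No document gives the prevalence or prognostic strength of the fall. The 5-point gain needs an odds ratio of 9; with a moderate factor the gain is about 1 point, and with none there is a loss of about 2. The fall is acute and leads to treatment at entry, which could weaken its link with status at day 180.
- **That every patient 10% down is close to an event.** The shared reference is explicit only for progressive CLAD. New CLAD, the natural event for BOS 0 and 0p patients, refers to an undefined baseline and needs two measurements.

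The objection that 40 patients are too few to adjust fits multi-covariate logistic regression better than this test, whose size stays near 5% even with four strata.

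**Conclusion.** The point holds as a minor, optional improvement. Section 7 leaves unused the factor on which randomization is stratified and a pre-treatment measurement that shares its reference with part of the endpoint. The consequence is limited to precision and to exposure to chance imbalance. On the assumptions above, the change in power runs from about −2 to +5 points, and nothing in the documents narrows that range. The firmer benefit is that, if the fall is strongly prognostic and the arms happen to differ, the pre-specified test keeps its error near 5%. The change does not repair the larger problem that 40 patients give about 37% power and not 80%.

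**What to change.** In section 7, pre-specify for the day-180 endpoint a Mantel-Haenszel test and a Mantel-Haenszel risk difference, stratified by BOS group as randomized (0 and 0p against 1 and 2) and by FEV1 fall at CARV infection (10% or more from the pre-CARV baseline, yes or no). Report the unadjusted chi-squared alongside. Do not add upper or lower tract infection as a further stratum, because the fall is part of that definition.

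Define the fall from an FEV1 taken before the first dose. Section 6.2 puts ± 10 days after its list of time points; if that window were read as covering the entry test, a value could post-date a first dose given as early as day 4 (7 − 3). State also whether the log-rank test uses the same strata; a stratified log-rank test was not examined here.

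The cost is analysis wording only: no new data, visits or change to patient care. The downsides are small strata and a possible loss of about 2 points of power if the fall proves not to be prognostic.

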6.1. Patient Symptom Score Card

Subjects will be asked to complete symptom score cards (Appendix 1) daily for 7 days following enrollment.

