4.6. Study Population and Eligibility Criteria

The study staff will prescreen/screen all lung transplant (LTx) recipients at the institution who develop respiratory symptoms suggestive of a CARV infection. The study will only enroll a patient if he/she can come to the medical center to receive study drug. In general, the study staff will consent patients who have undergone lung transplantation, and randomize study participants (consented patients) that develop post-transplantation CARV infection. Table 1 outlines specific study eligibility criteria for enrollment and randomization. A screening log will document limited information regarding patients that undergo screening but not enrollment. Case report form (CRF)/computer data entry system will capture reason(s) for exclusion.

Table 1. Eligibility criteria for enrollment in the study

Inclusion Criteria:

- Adult (≥ 18 years old)
- Single, bilateral, or heart-lung transplant recipient
- Confirmed infection with a community-acquired respiratory virus
 - Including: adenovirus, coronavirus, influenza A or B, respiratory syncytial virus (RSV), parainfluenza virus (PiV), human metapneumovirus (hMPV), and rhinovirus/enterovirus
- At least 6 months post-transplant, with completion of 6 month surveillance bronchoscopy if indicated
- Able and willing to give written informed consent and comply with study procedures (e.g. testing, treatment)
- Able to undergo randomization and initiate study drug within 10 days of CARV infection

Exclusion Criteria:

- BOS Stage 3 [pre-CARV baseline $FEV_1 < 50\%$ of personal reference]
 - Pre-CARV baseline: the average of the 2 most recent FEV_1 separated by at least 3 weeks and also occurring within the 6 months prior to the CARV infection
 - In the event that only a single FEV_1 is available within the previous 6 months, that value will function as the pre-CARV baseline
 - Personal reference: the average of the 2 highest post-transplant FEV_1 at least 3 weeks apart
- Requirement for mechanical ventilation at study entry
- Use of inhaled steroids at the time of CARV infection
- Any condition that in the investigator's opinion would preclude the patient's participation in a clinical trial
- Lack of available spirometric data within 6 months preceding CARV infection to establish a baseline FEV_1 and/or FVC
- Pregnancy
- Current participation in another interventional clinical trial

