4.8. Randomization

Eligible patients who develop a CARV infection after lung transplantation will need to provide written informed consent prior to study participation and will undergo randomization using a computer-generated method with a 1:1 ratio, and stratified by BOS stage (group 1: BOS stages 0 and 0p vs. group 2: BOS stages 1 and 2) to one of the treatment assignments: (1) inhaled beclomethasone, or (2) placebo. The site will aim to randomize patients within 7 days of identification of CARV infection.

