8.3. Informed Consent

Patients will be informed about the study and its purpose when a diagnostic nasopharyngeal swab for CARV is obtained. Eligible patients who have a positive swab result or a positive bronchoscopy specimen PCR for CARV will be approached by the study investigators. The consent process will involve a dialogue between the potential participant and the study staff. Study participation will require written informed consent from the patient. The study staff will not conduct study procedures prior to obtaining informed consent. Patients eligible for randomization will be informed that they may withdraw their consent and drop out of the study at any time point.

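### The seven daily symptom cards are counted from enrollment, not from first dose, so some or most of them can be completed before any study drug is taken

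*Combined protocol and SAP*

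**What the plan says.** Respiratory viral symptoms are a secondary objective (Section 4.3), and the symptom score is a secondary endpoint (Section 4.9.2). The only symptom measurement described is the card in Section 6.1, completed "daily for 7 days following enrollment".

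Dosing runs on another clock. For the active arm, Section 5.2.1 says: "The first dose will be administered 7 ± 3 days after CARV infection". For placebo, Section 5.2.2 says the first dose "will be administered 7 ± 3 days after CARV infection". Both give days 4 to 10.

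Four other statements bear on when enrollment happens:

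- Section 8.3 (consent): "Eligible patients who have a positive swab result or a positive bronchoscopy specimen PCR for CARV will be approached by the study investigators".
- Section 4.8 (randomization): "The site will aim to randomize patients within 7 days of identification of CARV infection".
- Section 4.6, Table 1 (eligibility): "Able to undergo randomization and initiate study drug within 10 days of CARV infection".
- Section 4.6 (text): "The study will only enroll a patient if he/she can come to the medical center to receive study drug".

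None of these sets the number of days from enrollment to first dose, and enrollment is not defined separately from consent or randomization. Section 7 plans a t-test or Mann-Whitney test for continuous secondary endpoints. It gives no rule for pre-dose card days and no baseline adjustment.

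**The concern.** A card completed before the first dose cannot reflect an effect of the drug. Averaged into a 7-day score, such cards pull the two arms together, by an amount that depends on each patient's gap between enrollment and dosing. Both arms share the same dosing window, so the expected result is dilution toward the null rather than bias in favour of one arm.

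At stake is the chance of seeing a short-term symptom benefit if there is one. The cards stop after 7 days and no later symptom measurement is described, so on-drug days lost from the card period are not recovered elsewhere. The primary endpoint and the safety data are not affected.

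**Working it through.** The plan gives no figure of its own on this point, so there is nothing to reproduce. The check is a day count followed by an illustrative power calculation.

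**Inputs**

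- Seven daily cards counted from enrollment (Section 6.1).
- First dose on day d = 4 to 10 after CARV infection (Sections 5.2.1 and 5.2.2).
- Enrollment on day e. The protocol does not state it; assumed range 0 to 10, and not later than d. The gap is g = d − e.
- 20 patients per arm (40 randomized 1:1, Sections 4.5 and 4.8).
- A card completed on the day of first dose is counted as on drug.

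**Two readings of the card days**

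- Reading A, the literal one: the first card is on the day after enrollment, so cards cover days e+1 to e+7. Pre-dose cards = g − 1 for g from 1 to 8, and 0 when g = 0.
- Reading B: the first card is on enrollment day, so cards cover days e to e+6. Pre-dose cards = g for g from 0 to 7.

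**Example.** Enrolled on day 1 and dosed on day 7, so g = 6.

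- Reading A: cards on days 2 to 8, of which days 2 to 6 are pre-dose: 5 of 7.
- Reading B: cards on days 1 to 7, of which days 1 to 6 are pre-dose: 6 of 7.

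**Permitted day pairs.** Enrollment on days 0 to 4 allows 7 dosing days each (35 pairs). Enrollment on days 5 to 10 allows 6, 5, 4, 3, 2 and 1 (21 pairs). The total is 56.

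| | Reading A | Reading B |
|---|---|---|
| At least 4 of 7 cards pre-dose | gap ≥ 5 days: 6+5+4+3+2+1 = 21 of 56 | gap ≥ 4 days: 7+6+5+4+3+2+1 = 28 of 56 |
| All 7 cards pre-dose | gap ≥ 8 days: 3+2+1 = 6 of 56 | gap ≥ 7 days: 4+3+2+1 = 10 of 56 |

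These are counts of combinations that the windows allow. They are not probabilities.

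**Illustrative power.** If the daily effect is constant from the first dose, the effect on the 7-card mean is the true effect times the on-drug share. That share is (8 − g)/7 under reading A (for g from 1 to 8) and (7 − g)/7 under reading B (for g up to 7).

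- Gap 3 days: 5/7 = 71% (A), 4/7 = 57% (B).
- Gap 6 days: 2/7 = 29% (A), 1/7 = 14% (B).

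At 0.8 SD under reading A, the diluted effect is 0.8 × 5/7 = 0.571 SD at 3 days and 0.8 × 2/7 = 0.229 SD at 6 days. Two-sample t-test, 20 per arm, two-sided 5%, noncentrality = diluted effect × √(20/2):

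| Assumed true effect | No gap | 3 days, A | 6 days, A | 3 days, B | 6 days, B |
|---|---|---|---|---|---|
| 0.5 SD | 34% | 20% | 7% | 14% | 6% |
| 0.8 SD | 69% | 42% | 11% | 29% | 6% |
| 1.0 SD | 87% | 60% | 14% | 42% | 7% |

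The effect sizes are assumptions, since the protocol gives none for symptoms. The calculation also assumes an unchanged SD of the mean score and the same gap for every patient.

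A milder case: if gaps were spread evenly over 0 to 3 days, reading A gives 0, 0, 1 and 2 pre-dose cards. The mean on-drug share is (7+7+6+5)/28 = 89%, and power at 0.8 SD is about 60% instead of 69%.

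**The case against.** The strongest reply is that enrollment and dosing may be one event. Section 4.6 enrolls only patients who can come in for study drug, and Section 5.1 sends the assignment to the pharmacist through the system used once eligibility is confirmed. A single visit for enrollment, randomization and dispensing is a plausible reading, and it gives no pre-dose cards. This stands as a possibility. But being able to come in is not a requirement to be dosed that day. Reading enrollment as randomization does not close the gap either: Section 4.8 sets only a target for the latest randomization day, while the first dose may come as late as day 10. If day 0 means symptom onset rather than a positive test, enrollment falls later and the gap shrinks. Appendix 1, the card itself, is not in the supplied text and may carry start instructions.

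A reader might also infer three stronger things that the documents do not support:

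- **Cards could start before infection.** Section 4.6 says: "In general, the study staff will consent patients who have undergone lung transplantation, and randomize study participants (consented patients) that develop post-transplantation CARV infection". But the cards start at enrollment, not consent, and Table 1 requires confirmed infection for enrollment. That sentence adds nothing here.
- **Most cards will be pre-dose.** The windows permit this, but do not show that it is planned or usual.
- **A null symptom result could not be interpreted.** The cards are daily, so pre-dose days can be separated at analysis wherever dose dates are known. Information is lost outright only for patients with all or nearly all cards pre-dose.

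**Conclusion.** The point holds as a weakness in the measurement rule. Section 6.1 starts the cards at enrollment, the first dose is timed from infection, and nothing links the two, so cards for a secondary endpoint can precede treatment. The size ranges from no loss with same-day enrollment and dosing to most or all of the cards with a long permitted gap. At an assumed 0.8 SD, a uniform 3-day gap would cut power from 69% to 42% on the literal reading, or to 29% if the first card is on enrollment day. These figures illustrate the sensitivity and do not predict this trial's power, because the actual gaps are not stated and would vary between patients. The harm is possible dilution toward the null on one secondary endpoint of a 40-patient pilot. It merits a cheap improvement and does not threaten the main result.

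**What to change.** In Section 6.1, tie the cards to first dose: one card on the day of first dose, completed before dosing, as baseline, then daily cards for 7 days after the first dose. In Section 7, state that the mean post-dose score will be compared between arms with the pre-dose score as covariate. Every card in the comparison is then on drug, whatever the permitted dosing day, and no dose, dosing window or clinical rule changes. If enrollment and first dose already coincide in practice, the new wording simply records that.

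The cost is one sentence in each section and about one extra diary page per patient (8 cards instead of 7). Symptoms early in the illness, before drug, would be recorded less completely; the documents do not show how much that matters.
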